make 80% of all health care decisions for the family, shared the SSE brochure with relatives.^{4,6,29,30}

The *long-term goal* of this research is to reduce melanoma mortality by improving self-management of early detection of melanoma. Reduced mortality cannot be proven without effective structured melanoma SSE with partner assistance. One way to achieve partner-assisted SSE is to deliver a uniform self-management program to women who self-identify as at-risk, perform SSE and seek appointments with HCPs for concerning moles. In the absence of ready physician access due to COVID-19, we will test the feasibility of at-home mole self-sampling with a non-invasive adhesive patch used to acquire surface cells of the mole. Our *primary objective*, assessing effectiveness of a SSE education with partner assistance among at-risk women, extends the evidence-based SSE intervention developed among melanoma survivors and their skin check partners (R01CA154908)⁶ and delivers the program to women who had a screening mammogram, which demonstrated the individuals' commitment to health promotion and cancer screening.

STUDY ENDPOINTS:

Aim 1

Primary outcome:

Effectiveness of TMD with SSE will be defined as SSE performance. Further measures of fidelity will be assessed by:

- a) extent of body checked,
- b) recruitment of a skin check partner,
- c) time between noticing a concerning mole, requesting a mole self-sampling kit, and seeking HCP care for a concerning mole, and
- d) SSE sustained by monthly performance over 4 months.

Secondary Outcome:

The effect of TMD with SSE on seeking health care comparing intervention vs control groups for:

- a) inappropriate HCP appointments and skin biopsies for benign conditions, and
- b) appropriate HCP appointments for the clinical diagnosis of atypical (dysplastic nevus) or rule out melanoma and biopsy performed.

Exploratory Aim

Proof-of-concept Outcome:

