Contact information for potential subjects, who will be women who had a screening mammogram from January 2, 2019 until February 28, 2020, will be obtained from the Northwestern Medicine Electronic Data Warehouse (EDW). Based on our experience, women with a history of breast cancer will be excluded because the focus of their health care is on treatment of breast cancer. Subjects will be emailed a recruitment email explaining the research study regarding skin cancer prevention and skin self-examinations. Subjects will receive a link to the online REDCap program that offers electronic consent, randomization, and self-reported surveys. After remotely enrolling in the study, and completing the baseline questionnaire, the subjects will be randomized 1:1 between intervention and control arms. Intervention arm participants will receive the SSE brochure. The SSE brochure discusses basic information about melanoma, how to identify a melanoma, the importance of a skin check partner, and gives a diary for tracking monthly changes in moles via a provided scorecard. The provided postcard maybe printed by the woman and affixed to a location in their homes to capture their attention and remind participants to perform SSE. Subjects will invite a skin check partner to help score the border, color, and diameter of a new and/or concerning mole(s) using a provided scoring system for their 4 months of study participation. While a skin check partner will be beneficial to perform SSE, a skin check partner is not an absolute requirement to participate in this research. The scoring system uses a scale of 1-3 (1= normal, 2= unsure, 3= not normal). In the brochure, color examples of normal and abnormal features illustrate the scoring rules. The decision rules about seeking health care are based on the cumulative score of three features of the mole: 3 = benign, stop checking the mole; 4-7 = check the mole in one month; 8-9 = make an appointment with a doctor to have the mole checked in about 2-3 weeks, which is the standard of care for evolving moles. In the absence of physician access (COVID-19), the decision rules used in our prior research will be modified to:
8-9= perform mole self-sampling to determine if the mole needs to be biopsied.

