Subjects in the intervention arm will monitor new and concerning moles for 4 months by doing monthly skin checks and partner-assisted skin checks (if applicable), record the scores on a scorecard provided in their SSE brochure, and complete the monthly online survey, which asks about changes in mole scores and potential anxiety associated with evolving moles. Subjects will also receive a monthly text message to their personal phone with SSE reminders.

If the subject indicates on their monthly survey or by communicating with the study team, in the form of an email and/or call, that the score of their mole has increased, three options on how to proceed will be offered to the subject. The three choices are as follows: a) continue monthly checking the mole for change, b) receive the mole self-sampling kit to obtain genetic analysis to guide the decision to seek health care, or c) seek an appointment with an HCP.

The mole self-sampling kit contains the materials, directions and a Fed Express or USPS Express mail envelop to overnight the kit to the DermTech laboratory.

Participants may request a kit by email or telephone call to the research team, who will send the kit by Fed Express or USPS Express mail. Within 3-5 business days, the DermTech laboratory will provide the results of the gene analysis online to the PI, [name], who will inform the participant with a written report stating:

- a) the mole is benign, and nothing further is needed or
- b) the mole needs to be biopsied.

If the initial sample has too few cells for analysis, then the participant will be invited to obtain another sample, instructions will be reviewed by telephone or by Facetime with the participant and an additional sample will be obtained.

Participants requiring a skin biopsy will be referred to a local HCP. The research team will develop a participant navigation system for triage to a local HCP, including surgical oncologists, dermatologists, and family practitioners. This triage system will be used to refer participants to schedule an appointment for the skin biopsy within 2-3 weeks. The genetic analysis of the mole will be provided in a letter to the HCP selected by the participant.

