Intervention participants who have selected the mole self-sampling kit will be invited to participate in a structured telephone exit interview. The exit interview will seek to obtain feedback from the participant on the process of mole self-sampling and gain feedback on study materials. Subjects will be asked, at time of consent, if the study team has permission to audio record the exit interview for purposes of data analysis. Subjects may opt out of the audio-recording portion of the study. The researcher will not share these recordings with anyone outside of the immediate study team. The recordings will remain in locked file cabinets and on computers with restricted and password protected access.

Anxiety will be assessed on monthly surveys. If enhanced anxiety regarding a concerning mole is indicated, a referral for psychological support will be made by PI, [name].

Out of the 500 women enrolled at each location, it is expected that 140 of the 1000 (14%) enrolled will identify a concerning mole.⁴

DATA AND SPECIMEN BANKING:

See Data Management. Specimens will not be banked.

SHARING RESULTS WITH PARTICIPANTS:

Results of the gene analysis from the cells captured by the adhesive patches will be provided to the PI, [name]. [name] will then inform the participant, in the form of a written report, if the mole is benign and nothing further needs to be done or if the mole needs to be biopsied. If requested, [name] will discuss the report with participants. Participants requiring a skin biopsy will be referred to a local HCP, who will receive the genetic analysis of the mole via fax from [name]. At the conclusion of the study, all participants will receive an email summary of the results.

The same process of sharing results applies to participants and their skin check partners who have a concerning mole to self-sample.

STUDY TIMELINES:

Subjects, both intervention and controls will be engaged with the research for 4 months. After 4 months of active engagement, follow-up communication will only occur via telephone or email to answer any incomplete questions on surveys or any questions that arise from evaluating the EHR of HCP visits regarding the concerning mole(s). All communication will be documented in the subject's file as a progress note.

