Design, Analysis, and Power Calculation with Target Enrollment Justification

For the RCT, participants will be randomly assigned to receive the SSE intervention or control (healthy lifestyle) in a 1:1 ratio. This will result in approximately 500 participants in each group. The primary analysis will be intent to treat, with data imputed one of two ways. First, we will run a “worse-case scenario” where all drop-outs will be assumed to not be performing SSE. Second, we will create 5 imputed data sets for missing data based on all available data and analyze with PROC MIANALYZE to obtain valid statistical inferences. From previous work, we expect at least 60% retention at 4 months.

We will use GLMM with a logit link to test if the intervention affects the rate of SSE, while adjusting for the repeated measures within individuals over the first 4 months. Using these repeated measures, and assuming an autocorrelation of 0.9, a total sample of 1000 would enable us to detect an increase from 80% of SSE in the control group to 86.3% in the intervention group. Assuming only 10% discordance, a sample of 500 control women provides 80% power to detect an increase of 7%, while the remaining 3% cease SSE. Additional fidelity measures in Aim 2 will be combined to score an overall standardized fidelity score at each time. If the mean fidelity score is 80%, a sample of 500 women provide enough information to produce a 95% Confidence interval with a width of 0.09. The sample for 500 intervention women provides 80% power to detect declining fidelity or sustainability of monthly SSEs as a standardized slope of 0.13. The secondary outcome of seeking HCP appointments for a necessary mole will be analyzed with generalized linear models, as described above, but considering the outcome as “any HCP appointment” during the study time frame. Previous data suggests that approximately 14% of women should contact HCP for an appointment, and our sample of 1000 women provides 80% power to detect a baseline rate in the control group as small as 21%.

Plans for securing the data is in the “provisions to protect the privacy interests of participants” section of the protocol.

PROVISIONS TO MONITOR THE DATA TO ENSURE THE SAFETY OF PARTICIPANTS:

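### The monthly fidelity score has no common basis across women: its only listed components include a mole-to-care time that about 86% are not expected to have and an item defined over the whole 4 months

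*Combined protocol and SAP*

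**What the plan says.** The section Design, Analysis, and Power Calculation with Target Enrollment Justification says: "Additional fidelity measures in Aim 2 will be combined to score an overall standardized fidelity score at each time". For a mean score of 80% it then claims that "a sample of 500 women provide enough information to produce a 95% Confidence interval with a width of 0.09". It adds that 500 intervention women give 80% power for a standardized slope of 0.13, either in fidelity or in the sustainability of monthly SSE. The same section expects at least 60% retention at 4 months.

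Objectives and Study Endpoints contain only Aim 1 and an Exploratory Aim. The single list of fidelity measures is in Study Endpoints under Aim 1, introduced by "Further measures of fidelity will be assessed by":

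- (a) how much of the body was examined;
- (b) whether a partner was recruited;
- (c) "time between noticing a concerning mole, requesting a mole self-sampling kit, and seeking HCP care for a concerning mole";
- (d) "SSE sustained by monthly performance over 4 months".

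Three other statements bear on these items:

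- Procedures Involved: "it is expected that 140 of the 1000 (14%) enrolled will identify a concerning mole".
- Study Interventions, on the choices when a mole's score has increased: "a) continue monthly checking the mole for change, b) receive the mole self-sampling kit", with a provider appointment as the third.
- Study Interventions, on item (b): "a skin check partner is not an absolute requirement to participate in this research".

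The document gives no scoring or weighting of the components, no rule for a component that does not apply to a woman, and no monthly version of item (d).

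**The concern.** A score meant to be averaged over 500 women and followed for decline month by month should mean the same thing for each woman at each month. Items (c) and (d) work against that.

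Item (c) exists only after a woman has noticed a concerning mole. A rule that combines all the items therefore leads to one of two results. Either only mole-finders have a score, or finders and non-finders are scored on different items, and a woman's score changes its make-up in the month she finds a mole. In the second case a month-to-month change can reflect the change of items as well as a change in fidelity.

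Item (d), as worded, summarises the whole period and so has no value at month 1, 2 or 3.

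At stake are the interpretation of the fidelity score and the two sample-size statements attached to it. If the choice is left open, it will be made after the data are seen.

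**Working it through.** **Inputs.** Mean 80%, n = 500, width 0.09, slope 0.13, power 80% and retention of at least 60% come from the analysis section. The 14% comes from Procedures Involved. Assumptions: two-sided 5% level; 14% in each arm; the standardized slope treated as a one-sample standardized effect; SD 0.40, because none is given. For a score on a 0 to 1 scale with mean 0.8, the largest possible SD is √(0.8 × 0.2) = 0.40, so the widths below are upper bounds.

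**1. The plan's own figures.** Width = 2 × 1.96 × 0.40/√n. Detectable slope = (1.96 + 0.84)/√n.

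- n = 500: width 1.568/22.36 = 0.070; slope 2.80/22.36 = 0.125. The slope agrees with 0.13 after rounding; the width does not agree with 0.09.
- Exact (Clopper-Pearson) and continuity-corrected intervals at n = 500 both give 0.072.
- A width of 0.09 at n = 500 would need an SD of 0.09 × 22.36/3.92 = 0.51, above the 0.40 maximum.
- A width of 0.09 corresponds to n = (3.92² × 0.16)/0.09² ≈ 304.
- n = 300 (60% of 500): width 0.0905; slope 0.162; power at slope 0.13 is 61%.

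So 0.09 fits about 300 women and 0.13 fits about 500. A one-sided test does not reconcile them (slope 0.111 at 500, 0.144 at 300). A 99% interval at n = 500 would give 0.092, but the plan says 95%. The origin of 0.09 cannot be settled from the document.

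**2. Women with a value for item (c).** 0.14 × 500 = 70, leaving 430 of 500 (86%) without one. At 60% retention, 0.6 × 70 = 42. Even if all 140 expected finders were in the intervention arm, 360 of 500 (72%) would have no value. The complete chain will be rarer than finding a mole, because continued monitoring is an offered choice.

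**3. If item (c) were required for a score.**

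| n | Width (upper bound) | Detectable slope | Power at slope 0.13 |
|---|---|---|---|
| 70 | 0.187 | 0.335 | 19% |
| 42 | 0.242 | 0.432 | 13% |

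With all 140 finders in the intervention arm, the width would be 0.133.

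**4. If item (c) were skipped when absent.** The number scored does not fall to 70, so the table does not apply. The cost is comparability: about 14% of women are scored on one more item than the rest, from whichever month they find a mole.

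**The case against.** The strongest reply is that this is an unspecified rule and not a broken score. A reader might infer that the score cannot be computed. The documents do not support that: SSE in a given month, extent of body examined and use of a partner can each be given a value for every woman who responds, and a percentage over the applicable items is computable. It is also an inference that items (c) and (d) enter the score, since the sentence points to an aim that does not exist. Both points stand. However, no other list of fidelity measures exists, and nothing in the document says that scoring is over applicable items.

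A reader might also infer that including item (d) makes the slope test circular. It does not. A constant whole-period value would only dilute a slope, and a monthly version is part of what the plan sets out to follow.

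Three further limits stand:

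- The slope claim has a second limb, sustainability of monthly SSE, which needs neither the composite nor item (c).
- The widths of 0.19 and 0.24 use the largest possible SD and discard every woman without a mole, which the plan does not say it will do. They are not forecasts.
- Response to a concerning mole can fairly be regarded as adherence, since acting on a mole's score is part of the taught decision rules. That supports reporting item (c), but not mixing it into a score that most women cannot have in full.

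**Conclusion.** The concern holds in a limited form. The reference to Aim 2 is wrong. Read against the only list available, the rule for combining the measures does not define the monthly score on a common basis for the 500 women. About 86% are not expected to have item (c), and item (d) has no single-month value as worded. If item (c) were required, the interval could be as wide as about 0.19 (n = 70) or 0.24 (n = 42), against a stated 0.09. These bounds rest on SD 0.40, 14% in each arm and, for 42, retention of exactly 60%.

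Independently of item (c), the two stated figures do not match a single sample size. Under the same formulas, 500 women give 0.070 and 0.125, and 300 give 0.0905 and 0.162.

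The sustainability limb of the slope claim and the primary between-arm analysis of SSE do not depend on the composite. This should be corrected, but it does not threaten the main comparison.

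**What to change.** - Change Aim 2 to Aim 1 in the analysis section.
- Build the monthly score only from items observable each month for every responding woman: extent of body examined, set to zero in a month without SSE, and partner used that month. State in advance the weights and whether that month's SSE performance is included.
- Report mole-to-kit-to-care time separately, among women with a concerning mole.
- Analyse sustained SSE over 4 months as its own outcome.
- Restate the interval width and the detectable slope on one sample size that reflects retention, and give the SD assumed. With 300 women and SD 0.40 these are 0.0905 and 0.162.

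The cost is a few sentences in the analysis section. No new data are needed, provided the monthly survey already asks about extent of body examined and partner use. The protocol does not list the survey items, so this should be checked.

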STU#: 00212165

PROTOCOL TITLE: Targeted Melanoma Detection with Skin Self-Examination During COVID-19 Restricted Physician Access

PRINCIPAL INVESTIGATOR:

[name]
Northwestern University Feinberg School of Medicine
Department of Dermatology
[name]
[name]
[contact]
[contact]

RESEARCH PERSONNEL:

[name], MS
[name], BS

STATISTICIAN:

[name]
Professor of Preventive Medicine
Northwestern University Feinberg School of Medicine

VERSION DATE:

April 2, 2020

NCT04420273

STUDY SUMMARY:

The purpose and overarching aim of this study is to reduce melanoma mortality by improving early detection of melanoma with skin self-examination among people who self-identify as being at risk. Self-management of melanoma detection with skin self-examination (SSE) depends on ready access to dermatologists when a concerning mole is detected. In March 2020, the Illinois stay at home order (COVID-19) removed ready physician access and prohibited non-essential health care. Additionally, there was uncertainty about when regularly scheduled health care would resume. This submission seeks to explore the feasibility of at-home non-invasive mole self-sampling for those with a concerning mole with the intention of providing recommendations about the need for the mole to be biopsied.

OBJECTIVES:

Aim 1: To assess the effectiveness of targeted melanoma detection (TMD) with SSE education delivered remotely to women who had a screening mammogram.

The effect of TMD with SSE education on a) SSE performance, b) identification of concerning moles, c) time between noticing a concerning mole, requesting a mole self-sampling kit and receiving health care, and d) SSE sustainability in comparison with controls will be assessed among women served by Northwestern Medicine in one rural community and one metropolitan community. Health care providers' (HCPs) clinical/pathologic assessment of concerning moles will be identified in the Northwestern Medicine electronic health record (EHR) system.

Exploratory Aim: To assess the feasibility of self-sampling concerning moles for gene assay.

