a printed brochure will be mailed. Participants will receive monthly reminders via email and text messaged to their personal phone to perform SSE, to encourage engagement and retention. In addition, a monthly REDCap survey will be sent to the subject's email. This monthly survey will include goal setting and reminders to engage a skin check partner to help check skin in hard to see areas and to assist with the monitoring of any concerning moles and new moles. Tracking of specific details and changes of concerning and new moles will be documented on the provided scorecard in the brochure. If the score of the mole increases, which is indicated on the monthly survey or via email and/or phone, three options on how to proceed with the concerning mole will be provided to the subject.

-Option 1 is to continue monitoring the mole monthly for change.

-Option 2 will be to perform mole self-sampling with the kit to collect a sample of surface cells of the concerning mole with four adhesive patches for gene analysis to help decide about seeking further health care for biopsy of the mole. Of note, physician collected samples tested for *LINC* and *PRAME* gene mutations differentiated melanoma and melanoma in situ from benign moles and were confirmed histologically with 91% accuracy.

-Option 3 will be to seek an appointment with a health care provider.

If mole self-sampling is selected, the kit with the subject number as ID (blinded for personal identifying information), directions, and postage for the kit to be sent to the company that created this self-sampling kit, DermTech, will be provided. Upon completing the mole self-sampling and mailing the specimen to the DermTech laboratory, it will take 3-5 days for the results to be provided to the PI, [name], in the form of a secure online portal. The subject will not obtain their gene test results from the DermTech laboratory. [name] will provide written test results to the participant with the option of discussing the results with a telephone call. A referral will be made to the HCP to perform a skin biopsy if needed. The DermTech self-sampling kit is approved for use but requires ordering by a licensed HCP, who will be [name], the PI.

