In order to complete this research before the end of the grant (March 2021), we need to have IRB approval in early May, which will allow EDW to build the lists of eligible subjects. Then we will enroll subjects remotely in June-August 2020 and follow them for 4 months with online surveys (Oct-Dec 2020). Finally, the EHR of HCP visits will be reviewed about 3-4 months after the completion of the last online survey. This additional period of EHR review (Feb 2021- March 2021) gives subjects time to obtain an appointment with their HCP and have a biopsy, if needed.

INCLUSION AND EXCLUSION CRITERIA:

Inclusion Criteria:

- Adult women (aged 18 and older) having a screening mammogram with no upper age limit, who had a screening mammogram from January 1, 2019 to February 28, 2020.
- Able to read English
- Vision enough to read a newspaper
- Self-perception of their potential melanoma risk
- Willing to perform SSE with a skin check partner
- Willing to complete monthly surveys for 4 months and receive monthly text messages to personal mobile phone
- Have home Internet access and smartphone with data plan
- Have access to Federal Express or US Postal Service Express Mail to send mole self-sampling kits
- Willing to allow the research team access to their electronic health record to abstract physician assessment of concerning moles, biopsy results and treatment
- Willing to provide up-to-date email address, mailing address and telephone number

Inclusion criteria of skin check partner to have mole self-sampled

- Male or female over the age of 18 years
- Able to read English
- Vision enough to read a newspaper

Exclusion criteria

- Women under the age of 18 years

- Women overburdened with other co-morbid diseases, medical treatments (e.g., chemotherapy), or cognitive impairment (e.g., by a stroke) as determined by the PI.
- Previous participation in SSE research previously which may be a confounding variable in data analysis

Exclusion criteria of skin check partner to have mole self-sampled

- Male or female under the age of 18
- Unable to read English

VULNERABLE POPULATIONS:

This study will not include the participation of vulnerable populations

PARTICIPANT POPULATIONS:

Accrual Number:	Category/ Group:	Consented: Maximum Number to be Consented or Reviewed/Collected /Screened	Enrolled: Number to Complete the Study or Needed to Address the Research Question
Northwestern Medicine: Prentice Women's Breast Center	Women ≥ 18 years old	500	400

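### Aim 1(d) promises SSE sustainability compared with controls, but the only sustainability analysis described is a slope within the intervention arm

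*Combined protocol and SAP*

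**What the plan says.** The Objectives section lists four effects under Aim 1. On the last it states: "d) SSE sustainability in comparison with controls will be assessed". Study Endpoints places the same item among the fidelity measures, as "SSE sustained by monthly performance over 4 months".

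The section Design, Analysis, and Power Calculation with Target Enrollment Justification is the only analysis text. It contains four relevant statements:

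- **Allocation:** "participants will be randomly assigned to receive the SSE intervention or control (healthy lifestyle) in a 1:1 ratio", giving about 500 women per arm, with at least 60% retention expected at 4 months.
- **Between-arm model:** a GLMM with a logit link for the effect of the intervention on the rate of SSE. The repeated measures are adjusted for; no month or arm-by-month term is named.
- **Sustainability:** "The sample for 500 intervention women provides 80% power to detect declining fidelity or sustainability of monthly SSEs as a standardized slope of 0.13".
- **Controls:** a separate calculation within the 500 control women, in which 7% take up SSE and 3% stop.

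Procedures Involved says that controls complete a monthly survey mirroring that of the intervention arm. It also says that this is expected to raise their awareness and may lead some of them to start SSE.

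**The concern.** The objective is a comparison between arms, and the sustainability sentence describes a test in one arm. The two quantities can disagree in either direction.

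If both arms decline together for any common reason, the one-arm slope reports failing sustainability although the effect of the intervention has not changed. If intervention women hold steady while controls catch up, the one-arm slope reports full sustainability although the difference between arms has gone. The second case is not far-fetched, because the protocol foresees control uptake.

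The GLMM fills only part of the gap. Averaged over 4 months, an effect that is constant and an effect that is large early and absent late can look the same. What is at stake is the interpretation of a stated objective; the primary test is not affected. If the comparison is left unspecified, the form of the sustainability analysis may be chosen after the data have been seen.

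**Working it through.** **1. Reproduce the stated figure.** Inputs from the design section: n = 500 intervention women and 80% power. Alpha, sidedness and the scale of the slope are not stated. I assume two-sided 0.05, in keeping with the 95% confidence level used nearby, and a slope in units of its between-woman SD.

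Detectable slope, one sample = (1.960 + 0.842)/√500 = 2.802/22.36 = **0.125**, which rounds to the printed 0.13. One-sided 0.05 would give 0.111, which does not match. So 0.13 is a one-arm figure.

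**2. What a between-arm slope contrast could detect.** With equal slope SDs in both arms, the detectable difference is 2.802 × √(2/n), and power for a difference of 0.13 is Φ(0.13/√(2/n) − 1.960).

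| n per arm | Source | Detectable difference | Power for 0.13 |
|---|---|---|---|
| 500 | all randomized | 0.177 | 54% |
| 400 | 800 completers in the Participant Populations table, split 1:1 | 0.198 | 45% |
| 300 | 60% retention | 0.229 | 36% |

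Detecting 0.13 between arms would need 2 × (2.802/0.13)² = 929 per arm with complete data. The stated 0.13 is therefore not power for objective (d). These figures treat the slopes as means; power from the logit model would differ somewhat.

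**3. Sensitivity of the one-arm slope to a shared trend.** The documents give no size for such a trend, so the values are assumed. With no waning specific to the intervention arm, the probability that the one-arm test rejects is approximately Φ(s√500 − 1.960):

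- s = 0.05: 20%
- s = 0.08: 43%
- s = 0.10: 61%

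A between-arm slope contrast would cancel a trend that is common on the model's scale.

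**4. Two illustrations (assumed rates).**

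- Intervention 90% to 82%, controls 84% to 76%: the one-arm change is −8 points, while the difference is 90 − 84 = 6 at the start and 82 − 76 = 6 at the end.
- Intervention constant at 86%, controls 80% to 86%: the one-arm change is 0, while the difference goes from 6 to 0.

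Scale matters in the first case. In log-odds the intervention arm falls by 2.197 − 1.516 = 0.68 and controls by 1.658 − 1.153 = 0.51, so a logit interaction is not zero even though the difference in points is constant. This is a reason to report monthly differences in rates as well as the model contrast.

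**5. The control calculation does not supply the comparison.** With 7% starting, 3% stopping and n = 500, the McNemar power is Φ[(0.04√500 − 1.960√0.10)/√(0.10 − 0.04²)] = Φ(0.875) = 81%. This agrees with the stated 80%, but it is a change within controls that the plan never sets against the intervention arm.

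**The case against.** The sustainability sentence is a power statement and does not exclude other analyses. Study Endpoints lists sustained SSE under fidelity, and for fidelity a within-arm slope is a reasonable quantity: do the women who were taught SSE keep doing it? That stands, and the slope should be kept for that purpose. It does not replace the comparison promised in the Objectives, and no other analysis is described that would provide it.

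Four stronger readings are tempting, and the documents do not support them.

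- **That the trial gives no answer to (d).** The GLMM compares SSE between arms over the same 4 months that define sustained performance. In the second illustration its average effect would shrink too. The answer is incomplete, not absent.
- **That seasonal or pandemic change will distort the slope.** Study Timelines puts enrollment in June to August 2020 and follow-up ending about October to December, so a shared trend is possible. No figure for one is given, and staggered entry partly separates study month from calendar month.
- **That the month-4 difference alone is the sustainability result.** A zero difference can arise with the habit fully maintained, if controls take up SSE. That number mixes persistence with control uptake.
- **That the monthly reminders are a flaw.** They are an openly stated part of the intervention ("Participants will receive monthly reminders via email and text messaged to their personal phone to perform SSE, to encourage engagement and retention"). Saying in the report that SSE was sustained under reminders is a matter of wording.

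**Conclusion.** The point holds as a mismatch between an objective and its analysis. Objective (d) is comparative. The only sustainability analysis described is a one-arm slope, and its 0.13 reproduces only as a one-sample figure. The GLMM covers average SSE over 4 months but not whether the arm difference lasts.

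The mismatch itself rests on the text and needs no assumption. The size of any resulting error cannot be stated: the shared trends and the illustrative rates above are assumed, and show only that the one-arm slope and the between-arm result can disagree. The precision figures (about 0.18 at 500 per arm, 0.23 at 300) rest on two-sided 0.05, 80% power, equal slope SDs in both arms and a slope scale that the plan does not define. This should be corrected, but it does not threaten the primary analysis.

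**What to change.** Keep the overall arm effect in the GLMM as the primary test. For objective (d), specify before the data are examined:

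1. Add month and arm-by-month to the logit GLMM.
2. Report the arm-by-month contrast and the between-arm difference in SSE at each month, including month 4, with 95% CIs.
3. Show each arm's own monthly SSE rates alongside, so that persistence in the intervention arm and uptake among controls can be told apart.
4. Run this under the same two missing-data analyses as the primary. When drop-outs are counted as not performing SSE, an arm with 60% retention cannot exceed 60% at month 4, so that version partly reflects retention and should be read beside the multiple-imputation result.
5. Keep the intervention-only slope as a descriptive fidelity measure, and label 0.13 as within-arm and not as power for (d).

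No new data are needed, because controls already complete the mirrored monthly survey. The cost is precision, as shown in the table in the working: power for a slope difference of 0.13 is 54% at 500 per arm and 36% at 300. The plan should state the detectable difference with retention included, and present (d) as an estimate with its interval.
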